8.6 Genetics

For TS:

For treatment naïve children with TS, a 30-cell (or more) lymphocyte chromosomal analysis result OR TS mosaicism CGH-array analysis result must be available prior to baseline (Visit 2) in the study. If analysis results are already available from previous analysis, the results from this analysis can be used. Otherwise, the analysis must be performed locally. The result will be collected as part of the Turner syndrome related information in the eCRF.

For NS:

If a genetic diagnosis is already available for a treatment-naïve child with NS prior to baseline (Visit 2), this result can be used for enrolment and no further testing is needed.

If a positive genetic test result for NS is not available, the analysis can be performed locally on the relevant genes listed in [Table 10-6](#). In this case, the result will be collected as part of the NS-related information in the eCRF. If genetic testing is not available at the local laboratory, the analysis must be performed by the engaged special laboratory, which will be providing the investigator with the result. The special laboratory results obtained should also be added in eCRF.

Once a relevant gene mutation has been identified, no further testing is required.

If all genes in [Table 10-6](#) have been tested and no genetic variant was identified, the participant can still be eligible if all remaining inclusion criteria and no exclusion criteria are fulfilled, as the participant may have a de-novo mutation associated with NS.

In the event of sample handling failure, a replacement genetic blood sample may be requested from the participant.

8.7 Biomarkers

No biomarkers are collected in this study.

8.8 Immunogenicity assessments

All anti-drug antibody (ADA) samples must be drawn prior to trial product administration if trial product administration is planned on the sampling day.

A tiered approach including screening of samples, confirmation of ADA as well as characterisation of cross-reactivity towards endogenous hGH and in vitro neutralising activity against the trial product will be used. To evaluate the impact of antibody formation, results of antibody analyses will be compared to PK and PD markers.

The investigator will not be able to review the results of the antibody measurements in relation to AEs as the results will not be available to the investigator.

ADA samples will be analysed no later than at end of study or if presence of neutralising ADA are suspected by investigator or sponsor. Participants who have had a positive in vitro neutralising antibody test result at the last visit will be offered an appropriate follow-up period until the antibody response remains unchanged, is decreasing or until the investigator or the sponsor decides that no further follow-up is warranted. The participants may be requested to have additional blood samples collected for follow-up analyses. If deemed relevant, i.e., due to an antibody relevant AE, unexpected low PK, or per request from the safety committee, specific samples may be analysed at other time-points during the study. The results may be reported as an amendment to the CSR.

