8.8.2 Assessment in case of suspicion of severe systemic hypersensitivity

In the event of a severe local and/or systemic hypersensitivity reaction possible or probably related to trial product, blood sampling for assessment of anti-somapacitan IgE antibodies as well as binding antibodies should be performed in relation to the reaction and no later than 1-2 weeks after the event.

In the event of a severe systemic hypersensitivity reaction to trial product it is recommended also to analyse a sample collected within 3 hours of the reaction for tryptase (total and/or mature tryptase) at the local laboratory. Moreover, a baseline tryptase measurement is necessary 1-2 weeks after the immediate severe hypersensitivity reaction due to individual variation in tryptase baseline concentration.

A follow up visit should be conducted 3-4 weeks after the allergic reaction with repeated blood sampling for assessment of anti-somapacitan IgE antibodies as well as binding antibodies and, if possible, also at a visit 3 months post the hypersensitivity reaction for assessing the persistence of the IgE response. Tryptase measurements are not required at the follow up visits.

9 Statistical considerations

If necessary, a statistical analysis plan (SAP) may be written in addition to the protocol, including a more technical and detailed elaboration of the statistical analysis. The SAP will be finalised before first participant first visit (FPFV).

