10.3.4.5 Follow-up of AE and SAE

The investigator is obligated to perform or arrange for the conduct of supplemental measurements and/or evaluations as medically indicated or as requested by Novo Nordisk to elucidate the nature and/or causality of the AE or SAE as fully as possible (e.g., severe hypersensitivity reactions, Hy's law). This may include additional laboratory tests or investigations, histopathological examinations, or consultation with other health care professionals.

If a participant dies during participation in the study or during a recognised follow-up period, the investigator should, upon request, provide Novo Nordisk with a copy of the autopsy report including histopathology.

New or updated information should be recorded in the CRF.

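### As worded, Section 8.8 withholds from the investigator the antibody results drawn because of a severe hypersensitivity reaction (binding antibodies directly, IgE by inference)

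*Protocol*

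**What the plan says.** Protocol Section 8.8 sets out tiered ADA testing and then the rule on access: "The investigator will not be able to review the results of the antibody measurements in relation to AEs", because "the results will not be available to the investigator". It sets end of study as the latest time for ADA analysis, with analysis also if neutralising antibodies are suspected. For an antibody-relevant AE, unexpectedly low drug levels or a safety committee request, "specific samples may be analysed at other time-points during the study". The paragraph ends: "The results may be reported as an amendment to the CSR". Section 8.8.1 places the anti-somapacitan antibody assay with a special laboratory and gives no reporting route to the site.

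Section 8.8.2 is a subsection of 8.8. Where a severe reaction has been given a causality rating of possible or probable, the instruction is that "blood sampling for assessment of anti-somapacitan IgE antibodies as well as binding antibodies should be performed in relation to the reaction", at the latest 1 to 2 weeks after the event. Sampling is repeated at 3 to 4 weeks and, "if possible, also at a visit 3 months post the hypersensitivity reaction for assessing the persistence of the IgE response". Tryptase is assigned to the local laboratory. No recipient is named for the IgE or binding-antibody results.

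Sections 7.1 and 7.1.1 leave stopping for safety reasons, and resuming after an AE-related pause, to the investigator. Section 10.3.4.5 obliges the investigator to carry out supplemental evaluations that are medically indicated or requested by the sponsor, "to elucidate the nature and/or causality of the AE or SAE as fully as possible (e.g., severe hypersensitivity reactions" and Hy's law being the examples given.

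**The concern.** The samples in 8.8.2 exist only because a child has reacted to the drug, and they are the drug-specific tests drawn for that event. The person who must judge whether to re-expose the child is told by the parent section that antibody results cannot be reviewed in relation to AEs. At stake is the later decision to resume treatment or stay off it, and the completeness of the causality work-up. The blood is drawn from the child in any case; the question is who may see the result.

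**Working it through.** No calculation applies. The check sets the relevant sections side by side.

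**1. What the rule covers.** The 8.8 sentence speaks of antibody measurements without qualification and ties the restriction to AEs. Binding antibodies are what the ADA assay measures, so the binding-antibody samples in 8.8.2 fall under it directly. IgE is not named in 8.8. Its coverage rests on two facts: 8.8.2 sits under 8.8, and 8.8.2 calls IgE an antibody. That is an inference.

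**2. Whether an exception exists.** Sections 8.8, 8.8.1 and 8.8.2, the laboratory appendix (10.2), the AE appendix (10.3) and the antibody paragraph in SAP Section 4.5 contain none. The early-analysis clause in 8.8 changes when a sample may be analysed. It does not change who receives the result.

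**3. Whether another route delivers the result.** Three were checked.
- Section 8.3.4 has investigators reviewing safety reports sent by the sponsor.
- Section 10.1.6.1 has an internal safety committee evaluating new signals.
- Section 10.1.6.2 has an independent data monitoring committee reviewing accumulated data.

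None says that an individual participant's antibody result goes to the treating investigator.

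**4. Who decides after a reaction.** The six mandatory stopping criteria in 7.1 do not include hypersensitivity. Hepatic events have an explicit restart rule in 7.1.1.1; hypersensitivity has none. The decision therefore falls to the investigator's discretion.

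**5. When the result could help.** Table 2-1 bases treatment of the reaction on local practice, and 8.8.2 recommends a tryptase sample within 3 hours at the local laboratory. The first antibody sample may be taken up to 1 to 2 weeks after the event and the repeat at 3 to 4 weeks. The results cannot guide acute care. They could inform only the later choice to resume or remain off treatment.

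**6. What release could disturb.** The study is open-label with one arm and no blinding at sites (6.3). AEs rated possibly or probably related form a secondary safety endpoint (Section 3, 9.3.3). Sampling under 8.8.2 follows only reactions already rated possible or probable, so the triggering event is already counted. Moving between those two ratings leaves the count unchanged; only a re-rating to unlikely would remove the event. Section 10.3.4.3 already lets the rating change on follow-up information. The primary endpoint counts AEs whatever their cause, so this does not affect it.

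**The case against.** The strongest opposing case is that the sentence belongs to the ADA text around it. It follows the tiered ADA method and precedes the statement on when ADA samples are analysed, so deferred analysis of scheduled samples is a natural reason for non-availability. On that reading, 8.8.2 is a separate procedure that merely omits a recipient. Further, no protocol step depends on an IgE or binding result, no section says such a result guides restarting, and the laboratory manual, which is not available for this review, may set a reporting route. Withholding is also stated openly and could protect investigator-rated causality.

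Much of this stands. The ADA context is why IgE is treated as an inference, and the documents do not show how much a result would change a decision. It does not remove the point: the sentence is general, is tied to AEs, and has no carve-out for samples taken because of one. If the manual does provide a route for these samples, 8.8 as worded contradicts it. The protocol never gives protection of causality ratings as its reason.

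Several stronger readings are tempting and are not supported.
- Section 10.2 requires review of all laboratory results, and Table 10-2 lists anti-somapacitan antibodies. A reader might infer a flat contradiction. But 8.8 can be read as a specific exception to a general duty, or the duty as covering only results the site receives.
- Sections 8.6 and 6.5.1 state that certain results or alerts reach the site. Those feed enrolment or a required dose reduction, so the absence of similar wording in 8.8 proves little.
- Section 8.8 lets neutralising-antibody follow-up run "until the investigator or the sponsor decides that no further follow-up is warranted", which sits awkwardly with the investigator not having the result. That clause concerns a positive result at the last visit and has no bearing on resuming treatment after a reaction.
- A reader might infer that results lie unseen until a study-report amendment. The early-analysis clause and the safety committee route show that they need not.

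**Conclusion.** The point holds as a minor, inexpensive patient-safety improvement. Section 8.8 states a rule, not merely a gap: as written, event-driven binding-antibody results, and by inference IgE results, are not available to the investigator who decides on resumption and must pursue causality. Frequency is low. Up to 50 participants are planned, the documents give no hypersensitivity rate, and there may be no such reaction.

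The conclusion assumes that 8.8 is read on its words and that the laboratory manual does not override it. It assumes only that the results could inform a later decision, not that they would determine one. A reader might infer that the rule puts a reacting child at immediate risk or biases the primary analysis; the documents support neither.

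**What to change.** In 8.8, limit the non-availability sentence to routine scheduled ADA samples. In 8.8.2, state that anti-somapacitan IgE and binding-antibody samples taken after a severe hypersensitivity reaction are analysed by the early-analysis route already in 8.8 and reported to the investigator and the safety committee when available. As a consistency edit only, add the matching exception for scheduled ADA samples to the general review sentence in 10.2, and align the laboratory manual. No treatment rule is proposed.

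The cost is a few sentences and occasional single-sample reporting by the special laboratory, with no extra blood or visits. The one statistical downside is a small chance that a released result influences the investigator's causality rating, and so the secondary endpoint of related AEs.

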8.8.1 Anti-somapacitan antibodies

Determination of antibodies against somapacitan will be performed by a special laboratory using a validated antibody assay. Confirmed anti-somapacitan antibody positive samples will be further tested for cross-reactivity to hGH and for in vitro neutralising effect in a validated neutralising antibody assay and by correlating to PK/PD.

8.8.2 Assessment in case of suspicion of severe systemic hypersensitivity

In the event of a severe local and/or systemic hypersensitivity reaction possible or probably related to trial product, blood sampling for assessment of anti-somapacitan IgE antibodies as well as binding antibodies should be performed in relation to the reaction and no later than 1-2 weeks after the event.

In the event of a severe systemic hypersensitivity reaction to trial product it is recommended also to analyse a sample collected within 3 hours of the reaction for tryptase (total and/or mature tryptase) at the local laboratory. Moreover, a baseline tryptase measurement is necessary 1-2 weeks after the immediate severe hypersensitivity reaction due to individual variation in tryptase baseline concentration.

A follow up visit should be conducted 3-4 weeks after the allergic reaction with repeated blood sampling for assessment of anti-somapacitan IgE antibodies as well as binding antibodies and, if possible, also at a visit 3 months post the hypersensitivity reaction for assessing the persistence of the IgE response. Tryptase measurements are not required at the follow up visits.

9 Statistical considerations

If necessary, a statistical analysis plan (SAP) may be written in addition to the protocol, including a more technical and detailed elaboration of the statistical analysis. The SAP will be finalised before first participant first visit (FPFV).

9.1 Statistical hypotheses

No hypotheses are planned to be tested in the study.

9.1.1 Multiplicity adjustment

Not applicable.

9.2 Analysis sets

The following participant analysis sets are defined within each sub-study:

Participant analysis set (PAS)	Description
Full analysis set (FAS)	All participants assigned to study intervention.
Safety analysis set (SAS)	All participants who are exposed to study intervention.

The full analysis set will be used to analyse endpoints related to the efficacy objectives and the safety analysis set will be used to analyse the endpoints and assessments related to safety.

For the efficacy analyses, participants will be included in the analyses according to the planned investigational intervention; whereas for safety analyses, participants will be included in the analyses according to the investigational intervention they actually received.

The following data points sets are defined:

Defined data points set (DPS)	Description
In-study	All observations from assignment to study intervention date up until visit 7 or last study contact, whichever comes first
On-treatment	All observed data from first study intervention and up until visit 7, last study contact, or 14 days after last administration, whichever comes first

The on-treatment data point sets represent data collected in the period in which a participant is considered exposed to IMP.

FAS and In-study are used to estimate the supportive secondary efficacy estimands for Height velocity, Change in Height SDS and Change in Height Velocity SDS.

FAS and On-treatment are used to present the supportive secondary efficacy estimands for Change in IGF-I SDS and Change in IGFBP-3 SDS.

Safety analysis set and On-treatment are used to present the primary estimand for the primary objective and all other safety data.

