1.3 Flowchart for extension period II

Procedure	Protocol Section	Extension period II							Discontinuation of treatment	Follow up
Visit		V19	V20	V21	V22	V23	V24	V25	V98	V99 ^a
Timing of visit (weeks)		169	182	195	208+2d	221	234	247		V98 +30d
Visit window (days)		±7	±7 exactly	±7	±2	±7	±7 exactly	±7		+5
PARTICIPANT RELATED INFORMATION AND ASSESSMENTS										
Discontinuation/Withdrawal criteria	7	X	X	X	X	X	X	X	X	
Concomitant medication	8.2	X	X	X	X	X	X	X	X	X
Pregnancy Test ^b	8.2.6	X	X	X	X	X	X	X	X	X
Pubertal status ^g	8.1.2		X		X		X		X	
Date of menarche ^c	8.1.2	X	X	X	X	X	X	X	X	X
EFFICACY										
X-Ray for bone age assessment	8.1.3				X				X ^f	
Body Measurements	8.1.1									
Height		X	X	X	X	X	X	X	X	

Procedure	Protocol Section	Extension period II							Discontinuation of treatment	Follow up
		V19	V20	V21	V22	V23	V24	V25		
Visit										
Timing of visit (weeks)		169	182	195	208+2d	221	234	247		V98 +30d
Visit window (days)		±7	±7 exactly	±7	±2	±7	±7 exactly	±7		+5
Body weight		X	X	X	X	X	X	X		
Sitting height (Turner syndrome & ISS)					X				X	
Pharmacodynamics	8.5									
IGFBP-3			X		X		X		X	
IGF-I			X		X		X		X	
Bioactive IGF-I			X		X		X		X	
Pharmacokinetics	8.4									

Procedure	Protocol Section	Extension period II							Discontinuation of treatment	Follow up
		V19	V20	V21	V22	V23	V24	V25		
Visit										
Timing of visit (weeks)		169	182	195	208+2d	221	234	247		V98 +30d
Visit window (days)		±7	±7 exactly	±7	±2	±7	±7 exactly	±7		+5
Somapacitan			X		X		X		X	
SAFETY										
Physical Examination ^d	8.2.1		X		X		X		X	
Vital Signs	8.2.2		X		X		X		X	
Electrocardiogram (ECG) (SGA & ISS)	8.2.3				X				X	
Electrocardiogram (ECG) (Turner- & Noonan syndrome)	8.2.3		X		X		X		X	
Transthoracic echocardiogram (TTE) (Turner syndrome)	8.2.4				X				X	
Transthoracic echocardiogram (TTE) (Noonan syndrome)	8.2.4		X		X		X		X	

Procedure	Protocol Section	Extension period II							Discontinuation of treatment	Follow up
		V19	V20	V21	V22	V23	V24	V25		
Visit										
Timing of visit (weeks)		169	182	195	208+2d	221	234	247		V98 +30d
Visit window (days)		±7	±7 exactly	±7	±2	±7	±7 exactly	±7		+5
Adverse Event	8.3	X	X	X	X	X	X	X	X	X
Laboratory safety assessments	8.2.5 10.2									
Haematology			X		X		X		X	
Biochemistry			X		X		X		X	
Glucose metabolism			X		X		X		X	
Lipids					X				X	
Hormones					X				X	
Antibodies			X				X		X	X

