2.3.3 Overall benefit-risk conclusion

Overall, the safety profile of somapacitan is similar to the well-known safety profile of daily growth hormone products e.g., Norditropin® and no new safety concerns have been found during the conduct of the somapacitan study program.

There are well known risks associated with administration of injectable medication³⁶ as well as procedural risks as described in [Table 2-1](#). In this study the risks associated with administration of trial product as well as the risks associated with the study procedures are expected to be comparable to what is seen in routine clinical practice.

More detailed information about the known and expected benefits and risks and reasonably expected adverse events (AE) of somapacitan may be found in the IB.

Taking into account the measures taken to minimise risk and burden to children participating in this study, the potential risks identified in association with somapacitan are justified by the anticipated benefits that may be afforded to children with SGA, TS, NS and ISS.

3 Objectives, endpoints and estimands

Table 3-1 Objectives and endpoints

Objectives	Endpoints		
Primary	Title	Time frame	Unit

 To evaluate the safety of once-weekly somapacitan in children, either naïve or non-naïve to GH treatment, within each of the four indications: SGA, TS, NS or ISS. 		Primary endpoint: Number of adverse events (AEs) From baseline (week 0) to week 26 Number of AEs	
		Secondary supportive safety endpoint: Number of adverse events (AEs) possibly or probably related to somapacitan From baseline (week 0) to week 26 Number of AEs	
Secondary	Title	Time frame	Unit

 To evaluate the long-term safety of once-weekly somapacitan in children, either naïve or non-naïve to GH treatment, within each of the four indications: SGA, TS, NS or ISS. 		Secondary supportive safety endpoint: Number of adverse events (AEs) From baseline (week 0) to week 156 Number of AEs	

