9.3.5 Other safety analyses

Safety laboratory assessments

Safety laboratory assessments (biochemistry, haematology, glucose metabolism, coagulation parameters (NS), and lipids) will be summarised by time of assessment for each indication, SGA, TS, NS or ISS. All abnormal values will be listed.

Vital signs

Vital signs (electrocardiogram, transthoracic electrocardiogram (TS, NS)) will be summarised by time of assessment for each indication, SGA, TS, NS or ISS. The investigator's evaluation of vital signs will be tabulated by time of assessment for each indication, SGA, TS, NS or ISS.

Antibodies

For confirmed anti-somapacitan antibody positive samples, the anti-somapacitan positive cross-reactivity to hGH antibodies and in vitro neutralising effect will be tabulated by time of assessment for each indication, SGA, TS, NS or ISS.

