##### **Vital signs**

Vital signs (electrocardiogram, transthoracic electrocardiogram (TS, NS)) will be summarised by time of assessment for each indication, SGA, TS, NS or ISS. The investigator's evaluation of vital signs will be tabulated by time of assessment for each indication, SGA, TS, NS or ISS.

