##### **Antibodies**

For confirmed anti-somapacitan antibody positive samples, the anti-somapacitan positive crossreactivity to hGH antibodies and in vitro neutralising effect will be tabulated by time of assessment for each indication, SGA, TS, NS or ISS.

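### The On-treatment set stops at visit 7 but is assigned to all safety data, so the laboratory, ECG, TTE and antibody summaries end at week 26 as written

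*Protocol*

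**What the plan says.** Protocol 9.2 and SAP 3 define two data points sets, In-study and On-treatment, and both close at visit 7 at the latest. On-treatment is "All observed data from first study intervention and up until visit 7, last study contact, or 14 days after last administration, whichever comes first". Its use is then fixed with no exception: "Safety analysis set and On-treatment are used to present the primary estimand for the primary objective and all other safety data". In between, the set is explained as follows: "The on-treatment data point sets represent data collected in the period in which a participant is considered exposed to IMP".

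The safety summaries are set out in Protocol 9.3.5 and SAP 4.5. Safety laboratory assessments "will be summarised by time of assessment for each indication, SGA, TS, NS or ISS. All abnormal values will be listed". For cardiac data the SAP says: "Vital signs (electrocardiogram, transthoracic electrocardiogram (TS, NS)) will be summarised by time of assessment for each indication, SGA, TS, NS or ISS" (the second item is presumably the echocardiogram). For antibodies, cross-reactivity and "in vitro neutralising effect will be tabulated by time of assessment for each indication, SGA, TS, NS or ISS". None of these paragraphs names a different data points set or a time limit.

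For adverse events only, Protocol 9.3.3 and SAP 4.3.2.1 define a longer endpoint by replacing 26 weeks with 156 weeks in the primary method.

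**The concern.** Dosing continues after visit 7, through extension period I to week 156 and, for some participants, through extension period II. A set that is meant to represent exposure but closes at week 26 contradicts its own explanation. Because the same set is assigned to all remaining safety data, the rule as written cuts the laboratory, ECG, TTE and antibody tables at week 26.

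The secondary objective in Protocol Section 3 is "To evaluate the long-term safety of once-weekly somapacitan in children", and Protocol 4.1 gives long-term safety as the purpose of extension period I. Protocol 4.2 says the extra monitoring in Turner and Noonan syndromes is there for cardiovascular safety. The study tests no hypothesis, so its descriptive safety tables are its main product. If the tables are run past week 26 anyway, nothing written says which extension-period laboratory, cardiac or antibody values count as on-treatment, for example those obtained after dosing has stopped. Protocol 2.1 allows separate database locks and reports by indication, so an unwritten rule could be applied differently across four reports.

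**Working it through.** The plan gives no figure to reproduce here. The check is to apply the rule, look for anything that overrides it, and measure the period excluded.

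**Inputs**
- End of On-treatment: the earliest of visit 7, last study contact, and last administration + 14 days (Protocol 9.2; SAP 3).
- Visit 7 = week 26 (Protocol 4.4).
- Main period 26 weeks, extension period I 130 weeks, extension period II up to 91 weeks (Protocol 4.1).
- Scheduled post-baseline visits to week 156: visits 3 to 17 (Protocol 1.2).
- Extension period II: haematology, biochemistry, and ECG and TTE in Noonan syndrome at visits 20, 22, 24 and 98; antibodies at visits 20, 24, 98 and 99 (Protocol 1.3).

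**1. Apply the rule.** For a participant who continues on treatment after week 26, last study contact and last administration + 14 days both fall after visit 7. The earliest of the three is visit 7, so the set ends at week 26 however long treatment lasts.

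**2. Look for an override.**
- Protocol 9.3.5 and SAP 4.5 name no other set.
- SAP 4.5.1 (exposure) and 4.5.3 (additional safety assessments) are marked not applicable.
- SAP 4.8 records no change to the protocol-planned analysis.
- The substitution of 156 for 26 weeks applies to adverse events only, and no matching set is defined even there.

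**3. Size of the excluded period.**
- To the end of extension period I: 26 + 130 = 156 weeks; (156 − 26)/156 = 130/156 = 83%.
- Scheduled visits to week 156: visits 3–17 = 15, of which visits 8–17 = 10; 10/15 = 67%.
- With the maximum extension period II: 156 + 91 = 247 weeks; (247 − 26)/247 = 221/247 = 89%. This applies to the protocol only, because the SAP is based on protocol version 3.0 and does not describe extension period II.

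These are shares of time and of all visits. Individual laboratory, ECG and TTE time points in extension period I were not counted, because the column alignment of that flowchart is not reliable in the text available.

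**4. Follow-up antibodies.** Visit 99 falls 30 days after last treatment. Since 30 > 14, these samples lie outside any set that closes 14 days after the last dose, even once the visit-7 limit is removed. They need their own rule.

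**5. The adverse event window.** Protocol 9.3.2 and SAP 4.2 count events to end of treatment or 14 days after the last dose, with no visit-7 limit. Protocol 4.4 and SAP 4.2.1 fix the primary endpoint at visit 7/week 26. The count is therefore determined, but the two descriptions should agree.

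**The case against.** The strongest reply is that the sets were drafted for the week-26 estimands and were never meant to bar later analyses. The explanation of On-treatment refers to exposure, and the summaries are by time of assessment. Section 9.3.6 also plans week-52 height and IGF parameters and near adult height to end of treatment, although both sets stop at visit 7. Adverse events have a usable rule in 9.3.2, carried to week 156. The only endpoint listed under the long-term safety objective is that adverse event count. Clinically significant laboratory or other safety findings must be reported as adverse events (Protocol 10.3.1). Investigator evaluation, sponsor surveillance and data monitoring committee review do not depend on this set.

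Much of this stands. It confines the problem to the non-adverse-event summaries, and it shows that no data are lost and that participant protection is unaffected. It is also fair that the percentages describe time and visits, not numbers of assessments. It does not cure the rule. Neither document limits the sets to a main-period report, and the assignment to all remaining safety data is explicit. The later parameters in 9.3.6 show that the visit-7 cut was carried too far; they do not show that it is absent. The adverse event window says nothing about how to classify a laboratory value, ECG, TTE or antibody result in the extension.

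**Conclusion.** The concern holds. Followed as written, Protocol 9.2 and SAP 3 end the laboratory, ECG, TTE and antibody summaries at week 26. That leaves out 83% of the time to the end of extension period I, or 89% for a participant who completes the maximum extension period II. The conclusion rests on the text of the two documents. The percentages assume a participant who stays on treatment for the full period.

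The effect is limited to descriptive long-term safety reporting. No test or error rate is involved, no stated figure is wrong, and nothing suggests that collected data would be discarded. The primary week-26 result is not threatened. It is a definition that should be corrected before the extension data are tabulated.

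**What to change.** 1. In Protocol 9.2 and SAP 3, state that the visit-7 limit on On-treatment applies to the week-26 endpoints only.
2. Add a full On-treatment set, from first dose to the earlier of last study contact and 14 days after last administration. Use it for the week-156 adverse event endpoint, cut at week 156, and for all other on-treatment safety summaries.
3. Present post-treatment follow-up antibody samples outside that set, labelled as such.
4. In Protocol 9.3.2 and SAP 4.2, add to the adverse event window that it ends no later than visit 7 for the week-26 endpoints. Record the changes in SAP 4.8.

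In the same revision, the In-study set should be given a matching extension for the week-52 height parameters and near adult height.

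The cost is text only, with no new data, visits or procedures. The SAP needs updating anyway to cover extension period II. Protocol 10.1.1 requires ethics approval for changes to the study design. This is an analysis-set definition, so the sponsor must classify it; it can go into the SAP first and into the protocol at the next amendment.
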